7.7 Day 8 Activities: Groups 1 and 2 Pre-dose

On day 8 the following information will be gathered and the indicated procedures will be performed PREDOSE:

- Record vital signs pre-dose.
- Perform 12-lead ECG taken in the supine position after at least 10 min of rest pre-dose.
- Complete pre-dose urine collection at 0 h (-12 h to 0 h) before bexagliflozin dosing for baseline UGE analysis and analysis of creatinine as described in [Section 6.6.2.3](#).
- Pre-dose plasma samples will be drawn for PK analysis as detailed in [Section 6.6.2.4](#).
- Pre-dose concomitant medications and adverse event information collected as appropriate.

7.8 Day 8 through 10 Activities: Group 1 Post-dose

On days 8 through 10 the following information will be gathered for group 1 and the indicated procedures will be performed after dosing:

- Dosing with first dose of subcutaneous exenatide 30 min prior to bexagliflozin tablets dosing will occur 1 h before the start of the breakfast as detailed in [Section 5.2](#).
- Dosing with second dose of subcutaneous exenatide 12 h after the first dose will occur 1 h before the start of the evening meal as detailed in [Section 5.2](#).
- Record vital signs at 4 h (day 8) and 48 h (day 10) postdose of bexagliflozin.
- Perform 12-lead ECG taken in the supine position after at least 10 min of rest at 4h (day 8) and 48 h (day 10) postdose of bexagliflozin.
- Plasma samples will be drawn for PK analysis as detailed in [Section 6.6.2.4](#) at 0.5, 1, 2, 3, 4, 5, 6, 8, 10, 12, 16, 24 (day 9), 36 (day 9) and 48 h (day 10) postdose of bexagliflozin.
- Urine collection in 12 h batches at 0 to 12 h and 12 to 24 h (day 8), 24 to 36 h and 36 to 48 h (day 10) for analysis of creatinine and glucose for UGE (PD) analysis as described in [Section 6.6.2.3](#).
- Post-dose concomitant medications and adverse event information is collected as appropriate.
- On day 10 perform a complete physical examination as described in [Section 6.3](#).
- On day 10 urine will be collected as described in [Section 6.6.2.2](#) for urinalysis.
- On day 10 blood will be drawn for hematology and serum chemistry as detailed in [Section 6.6.2.1](#).
- After completion of all day 10 activities the subject will be discharged. A follow up visit may be scheduled if clinically indicated. If a subject who withdraws consent prior to completion of all study activities, a follow up visit may be scheduled if clinically indicated.

Subjects who are terminated from the study for any reason after dosing has started must have the information and procedures shown for day 10 collected and completed and the reason for termination entered onto the case report form.

7.9 Day 8 through 10 Activities: Group 2 Post-dose

On days 8 through 10 the following information will be gathered for group 2 and the indicated procedures will be performed after dosing:

- Dosing with bexagliflozin tablets will occur 30 min before the start of the meal as detailed in [Section 5.2](#).
- Record vital signs at 4 h (day 8) and 48 h (day 10) postdose of bexagliflozin.
- Perform 12-lead ECG taken in the supine position after at least 10 min of rest at 4h (day 8) and 48 h (day 10) postdose of bexagliflozin.
- Plasma samples will be drawn for PK analysis as detailed in [Section 6.6.2.4](#) at 0.5, 1, 2, 3, 4, 5, 6, 8, 10, 12, 16, 24 (day 9), 36 (day 9) and 48 h (day 10) postdose of bexagliflozin.

- Urine collection in 12 h batches at 0 to 12 h and 12 to 24 h (day 8), 24 to 36 h and 36 to 48 h (day 10) postdose of bexagliflozin for analysis of creatinine and glucose for UGE (PD) analysis as described in [Section 6.6.2.3](#).
- Post-dose concomitant medications and adverse event information is collected as appropriate.
- On day 10 perform a complete physical examination as described in [Section 6.3](#).
- On day 10 urine will be collected as described in [Section 6.6.2.2](#) for urinalysis.
- On day 10 blood will be drawn for hematology and serum chemistry as detailed in [Section 6.6.2.1](#).
- After completion of all day 10 activities the subject will be discharged. A follow up visit may be scheduled if clinically indicated. If a subject who withdraws consent prior to completion of all study activities, a follow up visit may be scheduled if clinically indicated.

Subjects who are terminated from the study for any reason after dosing has started must have the information and procedures shown for day 10 collected and completed and the reason for termination entered onto the case report form.

7.10 Early Termination or Follow-up Procedures

Subjects who have completed study activities or have withdrawn consent and have received investigational product should have a follow-up examination if clinically indicated, including a complete physical examination, vital signs, ECG, urinalysis and clinical laboratory tests (hematology, and serum chemistry). The sponsor must be notified in the event that a subject withdraws or has been withdrawn from the study.

8 QUALITY CONTROL AND ASSURANCE

The clinical research facility will be monitored by the study monitor to ensure correct performance of the study procedures and assure that the study will be conducted according to the protocol and relevant regulatory requirements. CRF entries will be verified with the source documentation.

Quality control principles will be applied throughout the performance of this study by following the standard operating procedure (SOPs) of the contract research organization (CRO) and the sponsor. Review procedures will be implemented at the CRO for all documents that are generated in relation to the study.

9 PLANNED STATISTICAL METHODS

9.1 General Considerations

The statistical evaluation of pharmacokinetic and pharmacodynamic parameters will be conducted by the designated CRO. A detailed Statistical and Analytical Plan will be generated prior to initiation of the study. Statistical analysis will be performed using Statistical Analysis Software SAS (SAS Institute Inc., USA). Non-compartmental analysis will be performed using Phoenix[®] WinNonlin[®] 6.4 (Certara, USA).

9.2 Determination of Sample Size

The sample size for this study is not based upon formal statistical consideration. The sample size is considered adequate to characterize the PK of bexagliflozin, to assess potential drug-drug interactions and to provide safety and tolerability data on bexagliflozin when administered with exenatide.

9.3 Analysis Populations

Statistical analysis populations will include:

Safety: The safety population will include all randomized subjects who receive at least one dose of the drug. Subjects will be analyzed according to the treatment received.

PK: The PK population will include all randomized subjects who receive study drug and who have sufficient plasma bexagliflozin measurements to derive at least one PK parameter following dosing. The PK population will be used to summarize the PK parameters.

PD: The PD population will include all randomized subjects who receive study drug and will have had at least 2 batches of 12 h urine collection from which to calculate UGE measurement following dosing. The PD population will be used to summarize the PD parameters.

9.4 Demographics and Baseline Characteristics

Baseline characteristics will be descriptively summarized for all subjects in the safety and the PK or PD populations. No statistical tests will be performed.

9.5 Statistical Analysis of Pharmacokinetic Variables

To assess the effect of co-administration of exenatide on the PK of bexagliflozin, analyses of variance (ANOVA) using a linear mixed-effects model will be fitted to the natural logarithmic transformation of PK parameters of bexagliflozin (C_{max} , AUC_{0-t} and $AUC_{0-\infty}$). The linear mixed-effects model will include subject as a random effect, and treatment, period, and sequence as fixed effects. The 90% confidence intervals will be constructed for the ratio of the least squares (LS) geometric means of PK parameters (C_{max} , AUC_{0-t} and

AUC_{0-∞}) when bexagliflozin is dosed in combination with exenatide versus when dosed alone, with 80-125% defined as the lack of interaction boundaries.

Descriptive statistics for the PK parameters C_{max}, t_{max}, AUC_{0-∞}, AUC_{0-t}, AUC_{0-extr}, CL/F, Vz/F, λ_z, and terminal elimination half-life (t_{1/2}) will be tabulated by treatment. Means, standard deviations, medians, ranges (min, max) and geometric means and coefficients of variation will be presented for all PK parameters with the exception of t_{max}. Medians and ranges will be presented for t_{max}.

A listing of derived PK parameters of bexagliflozin by Subject and Treatment Period will be provided.

9.6 Pharmacodynamic Assessments

UGE and urinary creatinine will be assessed before first dosing and at the end of each treatment period.

UGE, including UGE_{t1-t2} and the total 0-24, 24-48 and 0-48 h UGE, will be determined. UGE_{t1-t2} (mg) will be derived from urine volume (V_{t1-t2}, mL) × glucose concentration (mg/dL) ÷ 100. Parameters normalized for urinary creatinine excretion will also be determined. UGE_{0-12h}, UGE_{12-24h}, UGE_{24-36h}, UGE_{36-48h} and the total 48 h UGE will be listed and presented in by subject listing and in summary tables for each group.

UGE in 12 h intervals up to 48 h post-dose, including the baseline, will be graphically presented against the corresponding treatment, bexagliflozin alone, and combination with exenatide.

The descriptive statistics will be used to describe any differences in UGE values between treatment groups.

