Statistical analysis will be performed using Statistical Analysis Software SAS (SAS Institute Inc., USA). PK parameters of bexagliflozin will be calculated using non-compartmental analyses (NCA) of plasma concentration-time data. To assess the effect of co-administration of exenatide on the PK of bexagliflozin, analyses of variance (ANOVA) using a linear mixed-effects model will be fitted to the natural logarithmic transformation of PK parameters of bexagliflozin (C_{max} , AUC_{0-t} and $AUC_{0-\infty}$). The linear mixed-effects model will include subject as a random effect, and treatment, period, and sequence as fixed effects. The 90% confidence intervals will be constructed for the ratio of geometric means of PK parameters (C_{max} , AUC_{0-t} and $AUC_{0-\infty}$) when bexagliflozin is dosed in combination with exenatide versus when dosed alone, with 80-125% defined as the lack of interaction boundaries.

Descriptive statistics for the PK parameters C_{max} , t_{max} , $AUC_{0-\infty}$, AUC_{0-t} , AUC_{0-extr} , CL/F, V_z/F , λ_z , and terminal elimination half-life ($t_{1/2}$) will be tabulated by treatment. Means, standard deviations, medians, ranges (min, max) and geometric means and coefficients of variation will be presented for all PK parameters with the exception of t_{max} . Medians and ranges will be presented for t_{max} .

Descriptive statistics on the PD parameters will also be performed. Descriptive statistics will be used to describe any differences in UGE values between treatment groups.

Date of Original Protocol: 19 April 2017

Prepared in: Microsoft Word 2010

TABLE OF CONTENTS

SYNOPSIS.....	2
LIST OF ABBREVIATIONS AND DEFINITIONS OF TERMS.....	9
1 INTRODUCTION	11
1.1 Bexagliflozin for the Treatment of Type 2 Diabetes Mellitus.....	12
1.1.1 Summary of Nonclinical Data with Bexagliflozin.....	12
1.1.2 Summary of Clinical Data with Bexagliflozin.....	12
1.2 Glucagon-like peptide 1 receptor agonists (GLP-1 RAs) and Exenatide	12
2 STUDY OBJECTIVES.....	14
2.1 Primary Objective	14
2.2 Secondary Objective	14
3 INVESTIGATIONAL PLAN.....	15
3.1 Overall Study Design and Plan.....	15
3.2 Rationale for Study Design and Control Group.....	15
3.3 Study Duration and Dates	16
4 STUDY POPULATION SELECTION	17
4.1 Study Population.....	17
4.2 Inclusion Criteria	17
4.3 Exclusion Criteria	17
5 STUDY TREATMENT(S).....	19
5.1 Description of Treatment(s).....	19
5.1.1 Study Drug.....	19
5.1.2 Exenatide.....	19
5.2 Treatment(s) Administered	19

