3.2 Rationale for Study Design and Control Group

The primary goal of the study is to assess the safety, tolerability, PK and PD of orally administered bexagliflozin tablets when it is concurrently administered with exenatide injection in healthy subjects.

This study is designed to be a two-period, two-treatment, crossover study with a 7-day washout period (>10 plasma apparent terminal elimination half-lives for both bexagliflozin and exenatide). The crossover study will allow direct comparison of two treatments in the

same subjects. Such an approach eliminates the influence of difference in subject characteristics seen in parallel group design. The primary route for excretion of exenatide is glomerular filtration and subsequent degradation of peptide bonds. Thus, drug interaction involving CYP450 and phase II enzymes are not expected between bexagliflozin and exenatide. However, because of slowing of gastric emptying, exenatide is expected to alter the absorption of orally administered concomitant medications especially when exenatide is administered prior to co-administered drug, typically resulting in a minor reduction of maximum plasma concentration (C_{max}) and a prolonged time of maximum concentration (t_{max}). Drug exposures are not expected to be significantly altered. In order to observe the maximal potential effect of exenatide on the absorption rate of bexagliflozin, bexagliflozin will be administered orally 30 min after subcutaneous exenatide injection, at 10 μ g bid (the highest dose approved for use in the United States), meanwhile, the highest dose used (10 μ g bid exenatide injection in the United States) or intended to be used (20 mg bexagliflozin tablets) clinically will be selected.

Previous studies showed that the PK parameters after multiple dosing were consistent with those after single doses for both bexagliflozin and exenatide. Thus a single oral dose of bexagliflozin tablets will be administered to healthy subjects in this study to evaluate the potential drug-drug interaction between bexagliflozin and exenatide. In this protocol, the effect of bexagliflozin on PK/PD of exenatide injection will not be measured since the PK of exenatide injection is unlikely to be affected by CYP450 and phase II enzymes involved pharmacokinetic interactions.

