2. STUDY OBJECTIVES

2.1 Primary Objective

To evaluate the effect of exenatide injection on the PK and PD of bexagliflozin tablets.

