The proportion of $AUC_{0-\infty}$ due to extrapolation (AUC_{extr}) will be calculated and expressed as a percentage. $AUC_{0-\infty}$ values will be considered unreliable estimates if the AUC_{extr} is greater than 20% and will be excluded from summary tables but will be listed.

CL/F will be calculated as $Dose/AUC_{0-\infty}$.

V_z/F will be calculated as $Dose/(\lambda_z \times AUC_{0-\infty})$.

$T_{1/2}$ will be calculated as $0.693/\lambda_z$.

Descriptive statistics for the plasma concentrations of bexagliflozin by Treatment and Timepoint will be provided. Listings of plasma concentrations by Subject Number, Treatment Sequence/Treatment, Period, and Timepoint will also be provided.

To assess the effect of co-administration of exenatide on the PK of bexagliflozin, an analyses of variance (ANOVA) using a linear mixed-effects model will be fitted to the natural logarithmic transformation of PK parameters of bexagliflozin (C_{max} , AUC_{0-t} and $AUC_{0-\infty}$). The linear mixed-effects model will include subject as a random effect, and treatment, period, and sequence as fixed effects. The 90% confidence intervals (CIs) will be constructed for the ratio of the least squares (LS) geometric means of PK parameters (C_{max} , AUC_{0-t} and $AUC_{0-\infty}$), when bexagliflozin is dosed in combination with exenatide versus when dosed alone, with 80-125% defined as the lack of interaction boundaries.

The ratios of geometric least squares means and corresponding 90% CI for the treatment comparison will be determined by exponentiating the mean differences between treatments on the logarithm scale. The intra-subject geometric CV%, $100\% * \sqrt{\exp(residual) - 1}$, where residual = the residual variance component and where exp is the natural exponential function, will be reported.

The appropriateness of the mixed model will be assessed through residual analyses. Any modifications required due to poor fit will be reported and executed.

Descriptive statistics for the PK parameters C_{max} , T_{max} , $AUC_{0-\infty}$, AUC_{0-t} , CL/F, V_z/F , λ_z , and $T_{1/2}$ will be tabulated by treatment. Means, standard deviations (SD), medians, ranges (minimum; maximum), and geometric means and coefficients of variation (CV) will be presented for all PK parameters with the exception of T_{max} . Medians and ranges will be presented for T_{max} .

A listing of derived PK parameters by Subject Number, Treatment Period, and Treatment will be provided.

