7.3 Pharmacodynamic Analyses

Urinary glucose excretion will be determined as a PD parameter at baseline and up to 48 hours.

Descriptive statistics of glucose concentrations, creatinine concentrations, UGE, and urinary glucose/urinary creatinine will be summarized by Treatment and Timepoint.

The quantity of glucose excreted in urine will be determined by multiplying the urine glucose concentration for each time interval by the volume of urine collected for the corresponding collection interval. The total 24-hour and 48-hour quantity of glucose excreted in urine will be calculated by adding the amounts collected during each interval.

PD data will also be reported in listings.

The PD parameters, UGE and UGE normalized by urinary creatinine, including $UGE_{t_1-t_2}$, in 12 hour and 24 hour increments, and total 24-hour and 48-hour UGE, will be determined. $UGE_{t_1-t_2}$ (g) will be derived from urine volume ($V_{t_1-t_2}$, mL) x glucose concentration (mg/dL)/100/1000.

UGE normalized by urinary creatinine will be derived by dividing the UGE for each interval by the corresponding urinary creatinine concentration.

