8. STATISTICAL ANALYSIS

8.1 General Data Handling Rules and Definitions

All data collected on CRFs will be provided in listings, except data collected only for confirmation of study entry criteria and for study administrative purposes. If any randomized subject is found to be without valid documented informed consent, that subject's data will be excluded from the report, except as necessary to document the error.

All statistical analyses will be conducted using SAS version 9.4 or newer.

Except where specified, all continuous variables will be summarized with descriptive statistics (the number of non-missing values, mean, standard deviation, median, minimum and maximum) and all categorical variables will be summarized with frequency counts and percentages, by treatment and treatment group. Unless otherwise specified, the mean and median will be displayed to 1 more decimal place than the original data, and standard deviation will be displayed to two more decimal places than the original data. All frequencies will be rounded to 1 decimal place.

Missing data will be maintained as missing unless specified otherwise. For variables where missing data is imputed, the analysis dataset will contain one variable with the imputed value and the original variable with missing maintained as missing.

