14. APPENDIX 2 SAS CODE FOR STATISTICAL ANALYSES

This section will be completed after examining the existing data and prior to the final signoff of this SAP.

Test	Table/Figure	SAS Codes for Modeling
ANOVA using a linear mixed-effects model.	PK endpoints requiring ANOVA.	
Analysis using PROC MIXED in SAS with SEQ, SUBJ, PERIOD, and TRTP identifying SEQUENCE, SUBJECT, PERIOD and TREATMENT variables. “Y” denotes the response measure (log (AUC), log (C_{MAX})). “KR” denotes Kenward-Roger method. “CL” denotes confidence limits.
 <pre> PROC MIXED METHOD=REML; CLASS SUBJ SEQ PERIOD TRTP; MODEL Y = SEQ PERIOD TRTP / DDFM=KR; RANDOM SUBJ(SEQ); LSMEANS TRTP / PDIF CL ALPHA = 0.10; ESTIMATE 'T/R' TREAT -1 1 / CL ALPHA = 0.1; RUN; </pre> 
Anti-log transformation to obtain the geometric means. “GEO” denotes geometric and “LS” denotes least square.
 <pre> DATA LSMEANS; SET LSMEAN GEOLSMEAN = EXP(ESTIMATE); RUN; </pre> 
Anti-log transformation to obtain the ratio of geometric means (point estimate) and 90% confidence interval (CI) – lower and upper bounds.
 <pre> DATA DIFFS; SET ESTIMATE; RATIO = EXP(ESTIMATE)*100; LOWER = EXP(LOWER)*100; UPPER = EXP(UPPER) * 100; RUN; </pre>

**15. APPENDIX 3 REFERENCE RANGES AND CLINICALLY RELEVANT CHANGES
FROM BASELINE FOR MARKED LABORATORY ABNORMALITIES**

<To be inserted>

16. APPENDIX 4 MOCKUP TABLES, LISTINGS, AND GRAPHS (TLGs)

Mockup tables, listings, and graphs are presented in a separate document.

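### UGE is half of the primary objective, but the plan gives no within-subject, period-adjusted estimate of the exenatide effect on it and no interval

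*Protocol*

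**What the plan says.** SAP 2.1 states one primary objective, with PK and PD unranked: "To evaluate the effect of exenatide injection on the PK and PD of bexagliflozin tablets". Protocol 2.1 agrees, and Protocol 6.8 names UGE as the PD parameter. Protocol 3.2 gives the reason for the design: "The crossover study will allow direct comparison of two treatments in the" same subjects.

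For PK, SAP 7.2 specifies the analysis: "The linear mixed-effects model will include subject as a random effect, and treatment, period, and sequence as fixed effects". It adds 90% CIs for the ratio of geometric LS means. SAP Appendix 2 labels its model code "PK endpoints requiring ANOVA".

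For UGE, the Protocol synopsis says: "Descriptive statistics will be used to describe any differences in UGE values between treatment groups". Protocol 9.6 repeats this, "The descriptive statistics will be used to describe any differences in UGE values between treatment groups", and adds by-subject listings, summary tables and a graph. SAP 7.3 says: "Descriptive statistics of glucose concentrations, creatinine concentrations, UGE, and urinary glucose/urinary creatinine will be summarized by Treatment and Timepoint". SAP 8.1 sets the default content of such summaries: "all continuous variables will be summarized with descriptive statistics (the number of non-missing values, mean, standard deviation, median, minimum and maximum").

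**The concern.** The design pays for a within-subject comparison, and the UGE plan does not use it. A by-treatment SD describes the spread of subjects under one treatment. It is not a measure of uncertainty for the exenatide effect, because the variance of a paired difference also depends on the within-subject covariance, which the summary tables do not show.

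The PD half of the primary objective would therefore be answered by two columns of means and SDs. A reader could see the direction of a difference but not whether the data exclude a large effect or are merely imprecise. The sample size has no formal basis (Protocol 9.2, SAP 3.5), so there is no design-stage precision statement to fall back on.

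**Working it through.** The plan states no UGE precision figure, so there is none to reproduce. The check compares the two halves of the objective and then sizes the loss.

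**1. What each half receives**

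| | PK | UGE |
|---|---|---|
| Within-subject model | Yes (SAP 7.2) | None |
| Period and sequence terms | Yes | None |
| Treatment contrast | Ratio of geometric LS means | None specified |
| Interval | 90% CI | None |
| Model code | Appendix 2 | None |

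**2. Inputs.** Planned subjects: 20, allocated 1:1, with a floor of 8 evaluable per group (Protocol 5.4, SAP 3.2). The documents give no UGE SD or within-subject correlation. Results are therefore in units of the total by-treatment SD, for assumed correlations ρ of 0.3, 0.5, 0.7 and 0.8, where ρ is the between-subject share of the variance.

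**3. 90% CI half-widths.** With n1 and n2 completers per sequence and n = n1 + n2:

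- Unpaired, all that the summary tables support: t(0.95, 2n−2) × √(2/n)
- Paired and period-adjusted: t(0.95, n−2) × √[0.5 × (1−ρ) × (1/n1 + 1/n2)]

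Example at 10 and 10: unpaired 1.686 × √0.1 = 0.533; paired at ρ = 0.5, 1.734 × √0.05 = 0.388.

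| Completers | Unpaired | ρ=0.3 | ρ=0.5 | ρ=0.7 | ρ=0.8 |
|---|---|---|---|---|---|
| 10 and 10 | 0.533 | 0.459 | 0.388 | 0.300 | 0.245 |
| 10 and 8 | 0.564 | 0.490 | 0.414 | 0.321 | 0.262 |
| 8 and 8 | 0.600 | 0.521 | 0.440 | 0.341 | 0.278 |

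At 10 and 10 the paired interval is 14% narrower at ρ = 0.3 (1 − 0.459/0.533) and 54% narrower at ρ = 0.8 (1 − 0.245/0.533). Break-even: 1 − ρ = (1.686/1.734)² = 0.945, so pairing gains for any ρ above about 0.055.

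**4. Period effect left in the raw difference of treatment means** (combination minus alone), as a share of the Period 2 minus Period 1 difference. Group 1 receives the combination in Period 2; Group 2 receives it in Period 1.

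- 10 and 10 complete: 10/20 − 10/20 = 0
- 10 and 8, complete pairs only: 10/18 − 8/18 = 0.111
- 10 and 8, Period 1 data of two Group 2 dropouts kept: 10/20 − 8/18 = 0.056

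A simulation of the last case (300 trials, ρ = 0.6, period effect 1, no treatment effect) gave a mean raw difference of 0.047 and a mean mixed-model estimate of −0.013, each with Monte Carlo standard error 0.012. The period effect carries into the raw means, as calculated, and the model removes it.

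**The case against.** The best defence is that descriptive PD is a deliberate choice, stated consistently in the synopsis, Protocol 9.6 and SAP 7.3. SAP 3.3 rules out formal testing. The PK interval has a defined use, comparison with the 80-125% boundaries, and UGE has no such boundary. This explains the asymmetry but does not remove the gap: the no-testing statement covers PK as well, and an interval is informative without a margin.

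Second, by-subject UGE listings are planned, so the paired data are not lost. That is true, and anyone holding the listings could compute a paired interval. But no such result is planned or reported, and the scale, the interval and the handling of incomplete collections would be chosen after the data are seen.

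Third, the table shells were not available, and Appendix 2 says it is still to be completed. However, SAP 1 describes the shells as layout, and SAP 4 says the analytic approaches are documented in the protocol and the SAP.

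Three limits stand. All the half-widths rest on assumed correlations. No decision is shown to turn on them. The choice of scale and lead interval is open to argument: a log-scale ratio would match PK, and slower absorption might show first in the 0-12 h batch.

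**Conclusion.** The concern holds. Neither document's text plans a within-subject or period-adjusted UGE contrast, or a standard error or interval for one, although PD shares the primary objective with PK. The main loss is precision: with all 20 subjects, an interval formed from the tables has a half-width of 0.53 SD, where the crossover would give 0.46 to 0.25 SD for correlations of 0.3 to 0.8. The point difference is not at risk with complete 10:10 data, because it can be read from the treatment means. Bias needs unequal sequences and a real period effect; with 10 and 8 completers, 5.6% to 11% of that effect would remain. PK remains fully interpretable, so this is an improvement that should be made rather than a flaw that invalidates the trial.

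**What to change.** In SAP 7.3, fit the SAP 7.2 model (fixed treatment, period and sequence; random subject) to untransformed UGE 0-24 h. Grams are the unit SAP 7.3 already uses, and 0-24 h is the total on which SAP 5.3 builds the PD population. Fit UGE 0-48 h as support. Report the LS-mean difference, combination minus alone, in grams with a 90% CI, labelled as estimation, without a test or a margin. If the sponsor prefers a ratio or another lead interval, give the reason and fix the choice in advance. Make the change by SAP revision before database lock, as SAP 10 provides, and note that it goes beyond Protocol 9.6.

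The cost is a few lines of SAP text and two model calls on data already being collected, with no new subjects, samples or visits. Incomplete totals drop out of the model, and the untransformed scale needs the residual check that SAP 7.2 already applies to PK.

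A separate minor item, which carries no weight here, can be settled in the same revision. Protocol 9.3 admits subjects with any two 12 h batches to the PD population, while SAP 5.3 requires the 0-12 h and 12-24 h batches. Align the two, and state that a 24 h or 48 h total is missing unless all its batches were collected.
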